1. PROTOCOL SUMMARY

1.1. Synopsis

Study Title: A Phase 2, randomized, open-label, 2-arm study comparing 2 intermittent dosing schedules of duvelisib in subjects with indolent non-Hodgkin lymphoma (iNHL)

Protocol Number: VS-0145-229

Phase: 2

Rationale: Dosing with duvelisib 25 mg twice daily (BID) has been shown to be efficacious in multiple Phase 1-3 studies including subjects with iNHL. The efficacy, safety and tolerability of this dose supported the US approval of duvelisib for the treatment of adult patients with relapsed or refractory (R/R) chronic lymphocytic leukemia (CLL)/small lymphocytic lymphoma (SLL) after at least 2 prior therapies and accelerated approval in adult patients with R/R follicular lymphoma (FL) after at least 2 prior systemic therapies. The current study will evaluate whether efficacy can be achieved and maintained, with acceptable or improved safety and tolerability, by inclusion of pre specified 2-week drug holidays in 2 different 25 mg BID schedules in subjects with R/R iNHL.

Objectives and Endpoints

Objective	Endpoint (see Section 9.4 for definitions)
Primary	
Evaluate the efficacy of duvelisib administered with prescribed drug holidays in subjects with iNHL	Overall Response Rate (ORR) according to the 2007 revised International Working Group (IWG) Criteria (Cheson 2007)
Secondary	
Evaluate supportive efficacy measures of duvelisib administered with prescribed drug holidays in subjects with iNHL	
ORR according to 2014 Lugano criteria (Cheson 2014) Note: all additional secondary response endpoints as well as progression-free survival (PFS), will be assessed separately using 2007 revised IWG criteria (Cheson 2007) and 2014 Lugano criteria (Cheson 2014)ORR, at 6, 12, 18, and 24 months after first dose of study interventionProgression-free SurvivalTime to Treatment Failure (TTF)Duration of Response (DOR)Overall Survival (OS)Lymph Node Response Rate (LNRR)Time to the First Response (TTFR)

Evaluate the safety and tolerability of duvelisib administered with prescribed drug holidays in subjects with iNHL	Adverse events (AEs), serious AEs (SAEs), vital signs, physical examinations, and clinical laboratory values
Characterize the pharmacokinetics (PK) of duvelisib and metabolite IPI-656 when duvelisib is administered with prescribed drug holidays in subjects with iNHL	PK parameters for duvelisib and metabolite IPI-656
Exploratory	
Evaluate Quality of Life (QoL) in subjects with iNHL treated with duvelisib with prescribed drug holidays	
 Eastern Cooperative Oncology Group (ECOG) Performance Score EQ-5D-3L questionnaire responses
Evaluate potential biomarkers of clinical efficacy and/or safety of duvelisib administered with prescribed drug holidays in subjects with iNHL	
 Blood assessments of immune cell populations, chemokines, cytokines, phosphorylated proteins, and/or circulating tumor ctDNA Fecal assessments of protein, DNA, and or RNA Tumor biopsy evaluation of biomarkers such as gene and copy number variation, RNA expression, protein expression, and/or immune cell content

Overall Design:
 
This is a Phase 2, randomized, open-label, 2-arm study designed to evaluate the efficacy and safety of prescribed drug holidays of duvelisib treatment in subjects with R/R iNHL who have received at least 1 prior systemic therapy.
 
Subjects will be stratified by number of prior therapies (1 or > 1), bulky disease status (longest diameter of baseline lesion < 5 cm or ≥ 5 cm) and time since last recurrence (≥ 24 months or < 24 months). Subjects will be randomized to Arm 1 or Arm 2 in a 1:1 fashion. Each treatment arm will be analyzed separately.
 
The study is a 2-stage design. For each arm: in the first stage, approximately 15 subjects will be enrolled. Responses will be assessed by the Investigator according to the 2007 revised IWG criteria (Cheson 2007) (primary endpoint) and 2014 Lugano criteria (Cheson 2014). The evaluation of the first stage will take place after the 15 enrolled subjects have been followed for a minimum of 3 cycles. If there are fewer than 6 responders (partial response [PR] or complete response [CR]) among the first 15 subjects in each arm, consideration may be given to stopping the arm. Otherwise, 36 additional subjects will be enrolled for a total of 51 per arm. Enrollment will be continuous between Stage 1 and Stage 2.
	

Number of Subjects:
 
Approximately 102 subjects will be enrolled and randomized at multiple sites globally. The study will employ a 2-stage approach with a planned enrollment of approximately 30 subjects for Stage 1 and up to approximately 72 additional subjects for Stage 2.
	

Intervention Groups and Duration:

- Arm 1: duvelisib 25 mg BID for one 10-week cycle followed by 25 mg BID in Weeks 3 and 4 of each subsequent 4-week cycles until disease progression, unacceptable toxicity, or withdrawal.
- Arm 2: duvelisib 25 mg BID on Weeks 1, 2, 5, 6, 9 and 10 of one 10-week cycle, then in Weeks 3 and 4 of each subsequent 4-week cycles until disease progression, unacceptable toxicity, or withdrawal.

[figure not shown]
It is anticipated that the study enrollment will occur over approximately 2 years. The last subject visit will occur 2 years after the last subject is randomized. If the study is ended prior to all subjects discontinuing treatment, any subject continuing to receive benefit will be provided the opportunity to continue to receive duvelisib. Long-term continued treatment may be provided via an expanded access program consistent with local regulations, such as the Secura Bio NPP.

Data Monitoring Committee: None.

Disclosure Statement: This is a parallel-group unblinded treatment study with 2 arms.

1.2. Schema

[figure not shown]
Figure 1: Treatment Scheme

Abbreviations: BID: twice daily.

Solid sections: duvelisib 25 mg BID; hashed sections: drug holiday. Subjects will be randomized 1:1 to Arms 1 and 2. Subjects will be assessed for disease response after approximately 10 weeks (i.e., within 7 days of the start of Cycle 2) and then within 7 days of the start of Cycles 4, 6, 9, 13, 17, and every 4th cycle thereafter until disease progression, unacceptable toxicity or withdrawal. (*): assessment of ORR after a minimum of 3 cycles of treatment in first-stage subjects (see [Figure 2](#)) to determine Stage 2 enrollment.

Figure 2: Two-stage Design for Each Arm

Abbreviations: CR: complete response; N: number of subjects; PR: partial response; ORR: overall response rate.

The decision to proceed to Stage 2 will be supported by the totality of data observed, including types of responses, safety data, and discontinuation rates. A treatment arm may also not proceed to the second stage if the totality of the data is compelling (e.g., accumulating enough data in Stage 1 to conclude the ORR exceeds 30%).

1.3. Schedule of Activities (SoA)

Table 1: Study Activities for Duvelisib Monotherapy (Cycle 1: 10 Weeks; Cycles ≥2: 4 Weeks)

Activity	Screening D-30 to D-1	Cycle 1					Cycle 2		Cycle 3+	EoT ^a	Safety F/U ^b 30d (+7) postdose		Notes
		D1	D14 (-3)	D29 (+3)	D43 (±3)	D57 (±3)	D1 (±3)	D14 (-3)					
Informed Consent	X												Potentially eligible subjects must sign an ICF prior to initiating any study specific procedures. Standard of care assessments that fulfill study eligibility requirements may be performed prior to subject signing the ICF.
Inclusion/Exclusion Criteria	X												
Randomization	X (D -7 to -1)												Subject must sign informed consent, meet inclusion/exclusion criteria, and complete all other screening activities prior to randomization.
Medical History, Demographics	X												Medical History includes histologic lymphoma diagnostic and prior treatment and response information, FLIPI-1 score
Archival Tumor Tissue	X												Tumor tissue is not required for enrollment, but should be submitted from all enrolled subjects, if available. Sample should be FFPE tissue and will be used to evaluate prognostic biomarkers.
Tumor Biopsy (optional)	X												If a transformation to a more aggressive subtype of lymphoma is suspected, a biopsy may be performed at Investigator's discretion. If this sample is collected, please see Archival Tumor Tissue instructions above.
Full Physical Examination	X	X											If performed within 7 days of C1D1, then screening results can be used for C1D1.
Focused Physical Examination			X	X	X	X	X	X	X	X			Disease-focused assessments including liver/spleen size, clinical assessment of tumor masses, and B symptoms.
Vital Signs	X	X	X	X	X	X	X	X	X	X			Vital signs measured in a semi-supine position after 5 minutes rest.
Computed Tomography (CT)	X									X			All subjects require CT or FDG-PET-CT scans. MRI may be used instead of CT scans if CT cannot

Activity	Screening D-30 to D-1	Cycle 1					Cycle 2		Cycle 3+	EoT ^a	Safety F/U ^b 30d (+7) postdose		Notes		
		D1	D14 (-3)	D29 (+3)	D43 (±3)	D57 (±3)	D1 (±3)	D14 (-3)	D1 (±3)						
Scans of the Chest, Abdomen and Pelvis		Day 1 of Cycles 2, 4, 6, 9, 13, 17, and Every 4th Cycle Thereafter (Window: Day -7 to Day 1 of Each Cycle)											be done, but the same method must be used throughout the study. A scan will be performed at the EoT if one was not performed within 30 days of the EoT Visit.		
Response Assessment									X				Response will be assessed separately using 2007 revised IWG criteria (Cheson 2007) and 2014 Lugano criteria (Cheson 2014)		
Bone Marrow Aspirate and/or Biopsy		As necessary to confirm CR											If a bone marrow/aspirate is performed within 60 days before C1D1 as part of standard of care, the pathology report will be provided to the Sponsor. If a radiologic CR according to 2007 revised IWG criteria (Cheson 2007) is observed during the course of the study, then a bone marrow biopsy should be done to confirm CR. The pathology report will be provided to the Sponsor.		
ECG (12-lead)	X												QTc measurements (as measured by triplicate readings) will use the Fridericia's correction method. Additional on-treatment or follow-up ECGs may be performed at the Investigator's discretion as clinically indicated.		
ECHO/ MUGA	X												ECHO or MUGA scan. Additional on-treatment or follow-up echocardiograms may be performed at the Investigator's discretion as clinically indicated.		
Concomitant Medications and Procedures	X	X	X	X	X	X	X	X	X	X					
AE/SAE Assessment	X	X	X	X	X	X	X	X	X	X					
Coagulation tests	X												Prothrombin time, partial thromboplastin time and international normalized ratio		
Viral screening	X												Hepatitis serology: HCV Ab, HBsAg, HBcAb. CMV/EBV serology or viral load. HIV test is not required if a prior negative test within 9 months is available.		

Activity	Screening D-30 to D-1	Cycle 1					Cycle 2		Cycle 3+	Safety F/U ^b 30d (+7) postdose	Notes				
		D1	D14 (-3)	D29 (+3)	D43 (±3)	D57 (±3)	D1 (±3)	D14 (-3)							
CMV Reactivation Monitoring			Subjects with a history of CMV infection/reactivation or viremia should be monitored for reactivation by PCR or antigen test at least monthly												
C-Reactive Protein	X	Obtain when Grade \geq 2 diarrhea or any colitis occurs													
Endocrine function	X										Free thyroxine and thyroid-stimulating hormone				
HLA Typing	X										Testing for HLA types A, B, C, DRB1, and DQB1. Do not need to perform if previous typing results are available.				
Serum hCG Pregnancy Test	X		X		X	X		X	X		For WCBP, a serum pregnancy test must be performed within 7 days of C1D1. At subsequent time points, serum testing is preferred but urine testing is allowed if a blood draw for other assessments is not performed. A positive urine test must be confirmed by a serum test.				
Clinical Chemistry, including Liver Function Tests	X	X	X	X		X	X		X	X		Liver function tests include LDH, serum ALT, serum AST, total and direct bilirubin, and ALP. Testing must be conducted, and results available, within 7 days prior to administration of first dose of duvelisib. Screening test results can be used for C1D1 if tests are performed within 7 days of C1D1.			
Immunoglobulin blood levels	X			X			X		X (even # cycles)			IgA, IgG, IgM			
Hematology	X	X	X	X	X	X	X		X	X		Hematology panel plus a 5-part differential. Testing must be conducted, and results available, within 7 days prior to administration of first dose of duvelisib. Screening test results can be used for C1D1 if tests are performed within 7 days of C1D1.			
Urinalysis	X	X		X			X		X	X		Qualitative analysis for protein performed at Screening, at C1D1, C2D1 and C6D1. If positive, quantitative analysis is needed if not previously noted as part of medical history. Testing must be conducted, and results available, within 7 days			

Activity	Screening D-30 to D-1	Cycle 1					Cycle 2		Cycle 3+	EoT ^a	Safety F/U ^b 30d (+7) postdose		Notes
		D1	D14 (-3)	D29 (+3)	D43 (±3)	D57 (±3)	D1 (±3)	D14 (-3)					
													prior to administration of first dose of duvelisib. Screening test results can be used for C1D1 if tests are performed within 7 days of C1D1.
ECOG Performance Status	X	X		X			X		X	X			If the ECOG Performance Status assessed at Screening is performed within 7 days of C1D1, the Screening assessment can be used and does not need to be repeated at C1D1 (predose).
EQ-5D-3L Questionnaire	X	X		X			X		X	X			Administered predose and prior to other procedures during treatment visits
Pharmacokinetic and Biomarker Assessments		X	X	X		X	X	X	X see note				For Cycles ≥ 3, obtain stool sample if subject has Grade ≥ 3 diarrhea or colitis. Request representative fragment of tissue and/or representative section of paraffin block from biopsy if taken for colitis or Grade ≥ 3 diarrhea.
	See Table 2 for detailed schedule												
Duvelisib Self-Administration Diary		X	X	X	X	X	X	X	X				First year on treatment only
Duvelisib Administration (Please see required and recommended prophylaxis in Section 6.6.1)		X (C1D14 AM dose in clinic)	X	X	X	X	X	X					Administration of the first dose should be scheduled to occur within 1 week after randomization. See Section 6.1 for dosing schedule.

Abbreviations: AE/SAE: adverse event/serious adverse event; ALP: alkaline phosphatase; ALT: alanine aminotransferase; AST: aspartate aminotransferase; BID: twice daily; CxDx: Cycle x, Day x; CMV: cytomegalovirus; CR: complete response; CT: computed tomography; EBV: Epstein-Barr virus; ECG: electrocardiogram; ECOG: Eastern Cooperative Oncology Group; ECHO: echocardiogram; EoT: end of treatment; FDG-PET: ¹⁸fluoro-2-deoxy-d-glucose-positron emission tomography; FFPE: formalin-fixed paraffin-embedded; FLIPI-1: Follicular Lymphoma International Prognostic Index; F/U: follow-up; HBcAb: hepatitis B core antibody; HBsAg: hepatitis B surface antigen; HCVAb: hepatitis C antibody; hCG: human chorionic gonadotropin; HIV: human immunodeficiency virus; HLA: human leukocyte antigen; ICF: informed consent form; iNHL: indolent non-Hodgkin lymphoma; IWG: international working group; LDH: lactate dehydrogenase; MRI: magnetic resonance imaging; MUGA: multi-gated acquisition; PCR: polymerase chain reaction; WCBP: women of childbearing potential.

- a. An EoT Visit will be performed for all subjects who permanently discontinue study intervention within 7 days following the decision to discontinue study intervention. EoT assessments need not be repeated if performed within the previous 14 days, or 30 days for CT scan.
- b. Safety follow-up visit to be performed 30 + 7 days from last dose. If possible, this visit should occur prior to the initiation of any subsequent anticancer therapy. This can be performed by telephone call if the subject does not require laboratory and/or other procedures related to any new or ongoing AEs, in which case a clinical visit will be required.

Table 2: Pharmacokinetic and Biomarker Sampling^{a,b}

Cycle	Study Day	Time Points	Whole blood for PK ^c	Whole blood for pharmacodynamic biomarkers (U.S. sites only)	Serum and plasma for biomarkers	Whole blood for immune cell analysis	Stool sample for biomarker analysis
1	1	Predose	X	X	X	X	X ^e
		1 hour (\pm 5 min) postdose	X	X			
		2 hours (\pm 10 min) postdose	X	X			
		4 hours (\pm 10 min) postdose	X				
	14 (-3) ^d	Predose	X	X			
		1 hour (\pm 5 min) postdose	X				
		2 hours (\pm 10 min) postdose	X				
		4 hours (\pm 10 min) postdose	X				
	29 (+3) ^d	Predose	X				
		1 hour (\pm 5 min) postdose	X				
		2 hours (\pm 10 min) postdose	X				
		4 hours (\pm 10 min) postdose	X				
	57 (\pm 3) ^d	Predose			X	X	
2	1 (\pm 3)	Anytime during visit			X	X	X ^e
	14 (-3)	Anytime during visit			X	X	
3+	Any	Anytime during visit					X ^e

Abbreviations: CR: complete response; CxDx: Cycle x Day x; PK: pharmacokinetics

- Any changes to this sampling plan (e.g., reductions in the number of sample collections) will be provided in the study lab manual.
- In addition to the samples shown in this table, provide (if feasible) a sample of any colon biopsies taken for colitis or Grade \geq 3 diarrhea
- PK sampling must occur on a dosing day. After a subject has had a dose reduction and received \geq 10 consecutive days of the reduced dose (not including scheduled dose holidays), PK sampling as shown for C1D1 will be repeated.
- On C1D14, C1D29 and C1D57, the morning dose of study medication will be administered in the clinic to accommodate PK and/or biomarker sampling.
- The C1D1 stool sample may be collected up to 7 days prior to C1D1. C2D1 stool samples may be collected up to 3 days prior to these visits. Stool samples may be collected either predose or postdose. Obtain additional stool sample if subject has colitis or Grade \geq 3 diarrhea.

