4. STUDY DESIGN

4.1. Overall Design

This is a Phase 2, randomized, open-label, 2-arm study designed to evaluate the efficacy and safety of alternative dosing schedules of duvelisib treatment in subjects with R/R iNHL who have received at least 1 prior systemic therapy. This is a multi-site global study.

Subjects will be stratified by number of prior therapies (1 or > 1), bulky disease status (longest diameter of baseline lesion < 5 cm or ≥ 5 cm) and time since last recurrence (≥ 24 months or < 24 months).

Subjects will be randomized to Arm 1 or Arm 2 in a 1:1 fashion.

- Arm 1: duvelisib 25 mg BID for one 10-week cycle followed by 25 mg BID on Weeks 3 and 4 of each subsequent 4-week cycles until disease progression, unacceptable toxicity, or withdrawal.
- Arm 2: duvelisib 25 mg BID on Weeks 1, 2, 5, 6, 9 and 10 of one 10-week cycle, then on Weeks 3 and 4 of each subsequent 4-week cycles until disease progression, unacceptable toxicity, or withdrawal.

The study has a 2-stage design (see [Figure 2](#)). For each arm: in the first stage, 15 subjects will be enrolled. Responses will be assessed by the Investigator according to the 2007 revised IWG criteria ([Cheson 2007](#)) (primary endpoint) and the 2014 Lugano criteria ([Cheson 2014](#)). The evaluation of the first stage will take place after the enrolled subjects have been followed for a minimum of 3 cycles. If there are fewer than 6 responders (partial response [PR] or complete response [CR]) among the first 15 subjects per arm, consideration may be given to stopping that arm. Otherwise, approximately 36 additional subjects will be enrolled for a total of 51 per arm. Enrollment will be continuous between Stage 1 and Stage 2. If fewer than 22 (43%) responders (PR or CR) are observed in 51 subjects, consideration may be given to concluding that the treatment schedule does not warrant further study in this population.

It is anticipated that study enrollment will occur over approximately 2 years. The last subject visit will occur 2 years after the last subject is randomized.

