4.2. Scientific Rationale for Study Design

Dosing with duvelisib 25 mg BID has been shown to be efficacious in multiple Phase 1-3 studies including subjects with iNHL. Data from the pivotal Phase 3 CLL/SLL study (DUO) and Phase 2 FL study (DYNAMO) showed that most tumor responses occurred by the end of Cycle 4 of duvelisib 25 mg BID treatment, and the majority of DIs for toxicity occurred primarily after 4 cycles. The post-hoc analysis of the DUO study showed that response to duvelisib was improved or maintained in most subjects who had ≥ 1 DI for > 1 week (84%) or > 2 weeks (82%), then followed by ≥ 3 weeks on duvelisib. PFS was also similar between subjects with ≥ 1 DI and those without DI for > 1 week or > 2 weeks within the first 3 months of therapy (median PFS: > 1 week, 17.8 vs 16.3 months; > 2 weeks, 17.8 vs 16.3 months) ([Flinn 2019](#)). These data support the hypothesis that prespecified 2-week drug holidays used in this study would not impact efficacy. Based on these results, the VS-0145-229 study will examine the effects of prespecified 2-week dose holidays on tumor responses (i.e., is uninterrupted dosing required in early cycles to

achieve responses, or can comparable tumor responses be achieved starting with alternating 2-week periods of dosing and holidays?) and safety/tolerability (i.e., will the holidays reduce the frequency, severity, and/or duration of AEs, allowing subjects to stay on treatment longer?).

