6.1. Study Intervention(s) Administered

Table 4: Study Intervention Arms

	Arm 1	Arm 2
Intervention Name	Duvelisib	
Type	Investigational Drug	
Drug Substance Description	White to off-white crystalline powder	
Dose Formulation	Capsule	
Unit Dose Strength(s)	25 mg 15 mg (dose reductions only)	
Formulation Excipients	Excipients (diluent, glidant, disintegrant, and lubricant) that are listed in the United States (US) Food and Drug Administration (FDA) Inactive Ingredients Database for approved drug products and/or Generally Regarded as Safe (GRAS).	
Dosage Level(s) and Frequency	25 mg BID for one 10-week cycle followed by 25 mg BID on Weeks 3 and 4 of each subsequent 4-week cycles until disease progression, unacceptable toxicity, or withdrawal	25 mg BID on Weeks 1, 2, 5, 6, 9 and 10 of one 10-week cycle, then on Weeks 3 and 4 of each subsequent 4-week cycles until disease progression, unacceptable toxicity, or withdrawal
Route of Administration	Oral	
Use	Experimental	
Investigational Medicinal Product (IMP) or Non-Investigational Medicinal Product (NIMP)	IMP	
Sourcing	Provided by the Sponsor	
Packaging and Labeling	Packaging and labeling will be prepared to meet all regulatory requirements.	
Current/Former Name(s) or Alias(es)	VS-0145, IPI-145	

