Section 1.3	Add C1D43 visit, with Hematology, Conmeds, focused PE, vitals, AEs, drug diary, and self-admin of drug	To provide for additional neutrophil count monitoring consistent with US Prescribing Information and ensure safety monitoring at this visit
Section 1.3	Added note to Clinical Chemistry, Hematology, and Urinalysis assessments that tests must be conducted, and results available, within 7 days prior to the first dose of duvelisib	To ensure that key laboratory parameters are assessed within a short time frame before first dose of study drug
Section 1.3 Section 5.2 Section 10.3	Removal of human T-lymphotrophic virus type 1 (HTLV-1) testing at Screening and from exclusion criterion #14	This testing is not relevant for this clinical study
Section 1.3 Section 8.1.1	Modified text describing requirements for imaging scans	To clarify that CT or PET-CT is required but MRI may be used instead of CT if CT cannot be done

Section(s)	Description of Change	Rationale for the Change
Section 1.3 Section 8.1.2 (Section 8.1.3 in prior version)	Changed bone marrow biopsy guidance for submission of available pathology reports from “most recent” to “within 60 days before C1D1”	If a patient had bone marrow biopsy/aspirate prior to the first dose of the study drug as a part of standard of care; the pathology report data within 60 days of C1D1 are more medically relevant than results from an earlier time point
Section 1.3 Section 8.2.1	Modified schedule of assessments to include Full Physical Examination (PE) at C1D1, and Focused PE and Vital Signs at every visit. Re-ordered SoA rows and text sections to present full PE, focused PE, and Vital Sign assessments sequentially. Align SoA notes and text descriptions.	To increase frequency of vital signs measurements and provide additional safety monitoring. Re-ordering and text alignment was done for clarity
Section 1.3 Section 10.3	Removed cortisol testing at Screening	Not needed for this clinical study
Section 1.3 Section 10.3	Added description of HLA types included in the HLA assessment at Screening	To provide additional assessment details for clarity
Section 2.1 Section 2.2 Section 4.2 Section 11	Added information to Rationale, Background, and Scientific Rationale sections, with supporting references	To provide justification for study design and population, as well as additional information on indication and available therapies

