#### 4.11.4 Clinical Laboratory Evaluation

Laboratory tests will be reported separately for hematology and blood chemistry.

For the purposes of presentation in both tables and listings, the following laboratory test results will be converted to the International System of Units (SI) before presentation: sodium, potassium, chloride, bicarbonate (or CO2), albumin, total protein, creatinine, uric acid, calcium, phosphorus, magnesium, glucose, total and direct bilirubin, alkaline phosphatase, red blood cell (RBC) count, hemoglobin, hematocrit, platelets, white blood cell count with 5-part differential

performed manually or by flow cytometry (lymphocytes, neutrophils, monocytes, basophils, and eosinophils), amylase, lipase, alanine aminotransferase (ALT), and aspartate aminotransferase (AST). Laboratory tests will be graded according to CTCAE Version 5.0 or higher.

If a laboratory test value is reported using a non-numeric qualifier (e.g., less than [<] a certain value or greater than [>] a certain value), the given numeric value will be used in the summary statistics, ignoring the non-numeric qualifier.

For laboratory tests graded by CTCAE, the following summary tables will be created by treatment arm:

- Summary of worst post-baseline value on treatment, regardless of baseline value according to the following categories:
  - Any grade
  - Grades 1 - 2
  - Grades 3 - 4
  - Grade 3
  - Grade 4
- Summary of worst post-baseline value on treatment that represents a worsening in grade from baseline according to the following categories:
  - Any grade
  - Grades 1 - 2
  - Grades 3 - 4
  - Grade 3
  - Grade 4

Laboratory tests with bi-directional grades (e.g., hyperglycemia and hypoglycemia) will be presented separately for each direction within each summary table.

For laboratory tests not graded by CTCAE, the following summary tables will be created by treatment arm:

- Summary of worst post-baseline value on treatment, regardless of baseline value according to the following categories:
  - Low (less than lower limit of normal)
  - Normal (greater than or equal to lower limit of normal and less than or equal to upper limit of normal)
  - High (greater than upper limit of normal)
- Summary of worst post-baseline value on treatment that represents a worsening from baseline according to the following categories:
  - Low (less than lower limit of normal)

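### In Cycle 1, two of Arm 2's three post-baseline liver panels follow a 14-day holiday and none is scheduled at Day 43, so transient elevations in Arm 2's second dosing block may be missed or graded lower

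*Protocol*

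**What the plan says.** Protocol Section 6.1, Table 4, gives Arm 1 "25 mg BID for one 10-week cycle followed by 25 mg BID on Weeks 3 and 4 of each subsequent 4-week cycles" and Arm 2 "25 mg BID on Weeks 1, 2, 5, 6, 9 and 10 of one 10-week cycle", after which both arms follow the same schedule.

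Protocol Section 1.3, Table 1, has one row, "Clinical Chemistry, including Liver Function Tests", for both arms, with the note "Liver function tests include LDH, serum ALT, serum AST, total and direct bilirubin, and ALP". It is marked at screening, C1D1, C1D14, C1D29, C1D57, C2D1, Day 1 of later cycles and end of treatment. The C1D43 cell is blank for chemistry and filled for hematology. The change log in Section 10.8.4 agrees with the current table: "Add C1D43 visit, with Hematology, Conmeds, focused PE, vitals, AEs, drug diary, and self-admin of drug".

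Protocol Section 4.2 states the tolerability question: "will the holidays reduce the frequency, severity, and/or duration of AEs, allowing subjects to stay on treatment longer".

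SAP Section 4.11.4 tabulates, by arm, "Summary of worst post-baseline value on treatment, regardless of baseline value according to the following categories" and adds boxplots at each scheduled visit. SAP Section 4.11.2 summarises by arm the treatment-emergent events of the first 10 weeks. SAP Section 4.11.2.1 and Appendix 1 define a transaminase event of special interest from preferred terms that include ALT increased and AST increased.

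**The concern.** A laboratory event without symptoms is found only when blood is drawn. If one arm is sampled after continuous dosing and the other after a two-week pause, the observed rates can differ for reasons of timing as well as for reasons of schedule.

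Cycle 1 is the only period in which the two schedules differ, so it is where a reader would look for an effect of early holidays. Transaminase elevation is an identified risk, reported in 22.8% of 588 monotherapy subjects (Protocol Section 2.3.1). A lower Arm 2 figure in the first 10 weeks could be a true benefit of the holidays, a product of when the samples were taken, or both. As sampled, Arm 2's second block cannot separate these.

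The gap also departs from the plan's own pattern. Every other Arm 2 dosing block in Cycle 1, and every block in both arms from Cycle 2, is followed by a scheduled panel at or near its end. The visit that would cover the second block already exists and already draws blood.

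**Working it through.** **Calendar check.** Protocol Section 9.2 equates 3 cycles with 18 weeks: 10 + 4 + 4 = 18. This reproduces, so C2D1 is study day 71 and C3D1 is day 99.

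**Dosing days in Cycle 1** (Section 6.1). Arm 1: days 1-70. Arm 2, weeks 1, 2, 5, 6, 9 and 10: days 1-14, 29-42 and 57-70, with holidays on days 15-28 and 43-56.

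**Visits against dosing** (windows from Table 1; days of dosing or holiday immediately before the visit). C1D1 is a predose baseline in both arms and is not counted.

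| Visit (window, study days) | Chemistry? | Arm 1 | Arm 2 |
|---|---|---|---|
| C1D14 (11-14) | yes | 13 days on | 13 days on |
| C1D29 (29-32) | yes | 28 days on | 14 days off (3 days back on if taken on day 32) |
| C1D43 (40-46) | no | 42 days on | 14 days on |
| C1D57 (54-60) | yes | 56 days on | 14 days off (11 off if day 54; 3 days back on if day 60) |
| C2D1 (68-74) | yes | 70 days on | 14 days on |

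At the late edge of the C2D1 window both arms have been off drug for 3 days, so that visit is symmetric. From C2D1 onward dosing and panels are the same in both arms.

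**Counts.**
- Post-baseline Cycle 1 panels that follow a holiday: 0 of 3 in Arm 1, 2 of 3 in Arm 2. Counting C2D1: 0 of 4 and 2 of 4.
- Arm 2 Cycle 1 blocks with a panel at or near their end: block 1 (D14) and block 3 (C2D1), so 2 of 3. Block 2 (days 29-42) has none.
- Interval D29 to D57 without scheduled chemistry, in both arms: 57 - 29 = 28 days; with windows, 54 - 32 = 22 to 60 - 29 = 31 days.

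**Can the size be derived?** No. The documents give neither onset nor recovery times for ALT or AST. As an assumption only, suppose the value falls exponentially off drug with half-life h days. The fraction left after 14 days is 2^(-14/h). The end-of-block value needed to read above 3 × ULN on D57 is 3 × 2^(14/h).

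| h (assumed) | Fraction left | Needed at end of block (× ULN) |
|---|---|---|
| 3 | 0.04 | 76 |
| 7 | 0.25 | 12 |
| 14 | 0.50 | 6 |
| 21 | 0.63 | 4.8 |

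The D57 panel could miss nearly all transient elevations or only the mildest, depending on h. That range is too wide to support an estimate.

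**How many subjects matter descriptively?** SAP Section 4.11.2 lists events with incidence at least 2% higher in Arm 1 (and at least 5% overall). With 51 per arm, 1/51 = 1.96% falls short of that margin and 2/51 = 3.9% passes it. A difference of two subjects is enough to meet the margin. That table covers the whole study, however, so later events dilute any Cycle 1 effect.

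**After adding chemistry at C1D43.** All three Arm 2 blocks would have a panel at or near their end (D14, D43, C2D1). Post-baseline panels through C2D1 that follow continuous dosing would be 5 of 5 in Arm 1 and 3 of 5 in Arm 2. The block 2 gap closes; the D29 and D57 asymmetry remains.

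**The case against.** The strongest case on the other side is that little depends on this.

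- **No inference is affected.** Protocol Section 9.4.1 and SAP Section 4.10.1 rule out formal comparison of the arms, and both arms take holidays from Cycle 2. This stands: the point concerns descriptive summaries only.
- **The worst-grade table has no Cycle 1 limit.** A subject is misclassified only if the worst elevation arises in block 2, subsides by D57, and is not matched at C2D1 or later. This stands, and that table is the least affected.
- **Other routes to detection exist.** Adverse events are assessed at D43, extra tests may be ordered at any time (Section 10.3), and known Grade 2-3 elevations are followed at least weekly (Table 5). This stands in part. Those routes need a symptom or a prior abnormal result, which a silent first elevation does not supply.
- **Arm 1 also has no panel between D29 and D57.** True. But Arm 1 doses through that interval and reaches D57 on drug, while Arm 2 reaches it after 14 days off.

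A reader might also infer stronger things that the documents do not support:

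- That Arm 2 elevations are in fact under-detected, or that a set share (such as the one block in three) is lost. Either needs an onset and recovery pattern that the documents do not give.
- That D29 and D57 are off-drug samples in Arm 2. Table 2's footnote has the morning dose given in clinic on those visits. They are readings at or near re-start, except D57 if taken early in its window.
- That a Grade 3 value at the end of block 2 would escape the Table 5 action. The schedule itself pauses dosing from day 43 for 14 days, and a panel falls around the restart. What could be lost is the weekly follow-up and the record of a first occurrence, which Table 5 treats differently from a later one.

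**Conclusion.** The concern holds as an asymmetry of ascertainment confined to the first 10 weeks. Two of Arm 2's three post-baseline Cycle 1 panels follow a 14-day holiday, against none in Arm 1, and block 2 has no scheduled liver test at its end. Transient, asymptomatic elevations in that block may be missed or graded lower. Any such effect would make Arm 2 look better.

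The counts rest only on the nominal calendar and visit windows, for subjects dosed as planned. The effect on observed rates cannot be sized from the documents. The outputs touched are the by-arm first-10-week events, the transaminase event of special interest, the by-visit laboratory displays and, less so, the worst post-baseline grade. The response-rate test is not touched. This is a cheap improvement, not a threat to the trial's primary conclusion.

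**What to change.** 1. **Protocol Table 1.** Add the chemistry and liver panel to the existing C1D43 visit in both arms, for subjects who have yet to reach it.
2. **SAP Section 4.11.4.** Add a by-arm Cycle 1 ALT/AST summary limited to scheduled visits at which both arms have just had about two weeks or more of continuous dosing: D14 and C2D1. Include D43 only if chemistry is scheduled there for all subjects; otherwise D43 values would come mainly from prompted tests and be selective.
3. **By-arm laboratory summaries.** Footnote that Arm 2's D29 and D57 values are post-holiday readings, at or near re-start of dosing.

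Items 2 and 3 can be done even if every subject has passed Cycle 1. They do not recover missed block 2 events, so that limitation should be stated alongside them.

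The cost is one chemistry tube at a visit that already draws blood, one extra table and one footnote. The observed Arm 2 elevation rate may rise.
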